#### **7.4.3 Subgroup Analysis**

[Analysis population: FAS, Analysis group: Randomization Arm]

- The estimate of the unadjusted risk ratio and 2-sided 90% confidence interval for the primary efficacy endpoint of AKI (AKI-SCr72h) proportion and secondary endpoints will be calculated by subgroups defined in [Section 7.8].
- In addition, the forest plot will be provided.
- For the continuous type subgroup factors, logistic regression model will be fitted for each continuous type subgroup factor 1 by 1. For each logistic regression model, response variable is primary or secondary endpoints (AKI-SCr72h, AKI-SCr7d, AKI-KDIGO72h, AKI-KDIGO7d, MAKE30 and MAKE90) and explanatory variables are treatment group, the subgroup factor and the interaction term of treatment group and the subgroup factor. The p-value of interaction will be calculated. The explanatory variables that will be used are listed as follows;
  - Left Ventricular Ejection Fraction (%),
  - AKIRisk Score ((ng/mL) $^2$ /1000) [Postsurgery],
  - Duration of CPB (hours),
  - Duration of Aortic Cross-Clamp (hours),
  - eGFR based on Serum Creatinine (mL/min/ $1.73\text{ m}^2$ ) [Baseline]

#### 7.4.4 Analysis of Exploratory Endpoints

[Analysis population: FAS, Analysis group: Randomization Arm]

The following analysis will be conducted for endpoint group 1.

- The proportion of subjects who meet the criteria will be analyzed using the CMH test with strata to control for baseline eGFR ( $< 45$ ,  $\geq 45$ ).
- The MH estimate of the adjusted common risk ratio and 2-sided 90% confidence interval will be calculated.
- If the proportion of subjects with baseline eGFR based on Serum Creatinine  $< 45$  mL/min per 1.73 m^2 for FAS is less than 10%, the above stratified analyses of CMH test and MH estimate of adjusted common risk ratio will be replaced with unstratified analyses of chi-square test and unadjusted risk ratio.

Group 1:

- All-cause mortality at day 30 (Visit 9)
- All-cause mortality at day 90 (Visit 10)
- Number of subjects needing RRT at day 30 (Visit 9)
- Number of subjects needing RRT at day 90 (Visit 10)
- Number of subjects with  $\geq 25\%$  sustained reduction in eGFR based on SCr at day 30 (Visit 9)
- Number of subjects with  $\geq 25\%$  sustained reduction in eGFR based on SCr at day 90 (Visit 10)
- MAKE30 with eGFR based on cystatin-C
- MAKE90 with eGFR based on cystatin-C
- Number of subjects with  $\geq 25\%$  sustained reduction in eGFR based on cystatin-C at day 30 (Visit 9)
- Number of subjects with  $\geq 25\%$  sustained reduction in eGFR based on cystatin-C at day 90 (Visit 10)
- Alternative derivations of proportion of subjects developing AKI using different definitions [[Table 3](#)] within 72 hours after T0. The stages will be used for subject developing AKI-SCr72h.
  - All stages AKI-UO (AKI-UO stage 2 or stage 3)
  - AKI-UO stage 3
  - AKI-SCr stage 2 or 3
  - AKI-SCr stage 2 or 3 and/or AKI-UO stage 3
  - AKI based on Cystatin-C, defined as an increase of  $\geq 10\%$  of baseline serum cystatin-C [[KDIGO, 2012](#)]

- Alternative derivations of proportion of subjects developing AKI using different definitions within 7 days after T0.
- AKI-SCr5d
- AKI-KDIGO5d
- Proportion of subjects with AKI as defined by a 50% or higher reduction in eGFR based on the Cystatin-C equation within 72 hours after T0.
- Proportion of subjects with AKI as defined by a 50% or higher reduction in eGFR based on the Cystatin-C equation within 7 days after T0.
- Proportion of subjects that have a reduction of NC AKIRisk score 24 hours after T0 (visit 3) to or below  $0.3 \text{ (ng/ml)}^2/1000$
- Proportion of subjects with renal recovery, defined as a SCr value at hospital discharge equal to or lower than that at baseline

The following analysis will be conducted for endpoint group 2.

- Descriptive statistics will be presented.
- The endpoint will be analyzed using the Wilcoxon-test.

Group 2:

- Number of hospital days during initial hospitalization
- Number of ICU days during initial hospitalization
- Total number of hospital days up to day 90
- Total number of ICU days up to day 90
- Duration of AKI based on AKI stage using SCr (Duration of AKI-SCr72h and Duration of AKI-SCr7d)

The following analysis will be conducted for endpoint group 3.

- The number and percentage of category will be presented.
- The endpoints will be analyzed using the Wilcoxon-test.

Group 3:

- Severity of AKI within 72 hours after T0
- Severity of AKI within 7 days after T0
- Number of readmissions to ICU (use “0 Times”, “1 Time”, “2 Times” and “3 Times or More” as category)
- Number of readmissions to hospital (use “0 Times”, “1 Time”, “2 Times” and “3 Times or More” as category)

The following analysis will be conducted for endpoint group 4.

- Time to event will be analyzed using Kaplan-Meier method. Kaplan-Meier estimator (1st Quartile, Median, 3rd Quartile, their 90% confidence intervals [CIs] and Range) will be presented. For AKI-SCr72h, subjects without developing AKI-SCr72h will be censored at the date of Visit 5 (Day 4, 72 hours after T0) or at the date of discontinuation if the subjects discontinue before Visit 5. For AKI-SCr7d, subjects without developing AKI-SCr7d will be censored at the date of Visit 8 (Day 7/DoD), at Day 7 if the Visit 8 (Day 7/DoD) assessment was not performed but still in the study or at the date of discontinuation if the subjects discontinue before Visit 8. For ventilator weaning, subjects who discontinued the study without ventilator weaning will be censored at the date of discontinuation.
- Time to event will be analyzed using the log-rank test.
- Hazard ratio and its 90% CI will be presented Based on Cox proportional hazards model with treatment as the only explanatory variable.

Group 4:

- Time to AKI-SCr72h
- Time to AKI-SCr7d
- Time to ventilator weaning, defined as the time from T0 to extubation (i.e., removal of the endotracheal ventilation tube)

The following analysis will be conducted for endpoint group 5.

- Descriptive statistics for the variables and changes from baseline at each visit will be presented.
- Mean difference between treatment groups for change from baseline and its 90% CI will be calculated at each visit and t-test will be conducted.
- Mean (+/- SD) plot for the variables and change from baseline will be produced.

Group 5:

- APACHE-II
- SCr, Cystatin-C, eGFR based on SCr and Cystatin-C, kidney injury molecule-1 (KIM1) and AKIRisk Score (For AKIRisk Score, postsurgery value will be used as baseline. If AKIRisk Score at postsurgery is recorded several times in eCRF, the last score will be used as the value at postsurgery.)

The following analysis will be conducted for endpoint group 6.

- Descriptive statistics for the variables will be presented.
- Mean difference between treatment groups for the variables and its 90% CI will be calculated and t-test will be conducted.

Group 6:

- AUCSCr72h
- AUCSCysC72h
- AUCSCr7d
- AUCSCysC7d

The following analysis will be conducted for other endpoints.

- EQ-5D-5L
  - Descriptive statistics for the EQ-5D-5L VAS score and changes from baseline at each visit will be presented for each treatment group. In addition, the descriptive statistics will be presented by subgroups of AKI-SCr72h (Yes/No) and AKI-SCr72h stage 2 or 3 (Yes/No)
  - Mean difference between treatment groups for the EQ-5D-5L VAS and its 90% CI will be calculated and t-test will be conducted.
  - For the EQ-5D-5L qualitative domains, the number and percentage of subjects in each response level value will be reported by visit.
  - Mean (+/- SD) plot for EQ-5D-5L VAS score and change from baseline will be produced.

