#### *Follow-up*

It is assumed that the subjects will be in the hospital up to at least 1 week after the surgery. On days 5, 6 and 7 after T0 (visits 6, 7 and 8, respectively) applicable assessments will be performed to assess study endpoints, including AKI (based on SCr). After end of all the procedures of visit 5, subjects can be discharged at the discretion of the investigator. If the subject is discharged before day 7, visit 8 will be done on the day of discharge and no site visits are required after discharge up to day 7. If the subject is discharged after day 7, visit 8 will be done on day 7 and no additional assessments are required after day 7 up to discharge, but the last result of SCr before discharge from local laboratory testing will be collected. Following day 7 (visit 8) or discharge, subjects will be followed up on day 30 (visit 9) and 90 (visit 10) following surgery. On visits 9 and 10, a composite endpoint of major adverse kidney events (MAKE) (all-cause mortality, renal replacement therapy [RRT] and/or  $\geq 25\%$  sustained reduction in eGFR) will be assessed.

Total number of hospital days and ICU days during initial hospitalization will be recorded. If the subjects are readmitted to hospital for any reason during the 90 follow-up days, the total number of hospitalizations and number of days hospitalized through day 30 and 90 will be recorded.

*Observational Cohort*

If at randomization NC is negative (AKIRisk score is  $\leq 0.3$  (ng/mL) $^2/1000$ ) at all assessments between 2 and 22 hours after T0, the subject cannot be randomized. These subjects will be included in the observational cohort. The rationale for following the subjects in the observational cohort is to further evaluate the AKIRisk score, as well as other risk factors (including clinical characteristics and biomarkers) for AKI and MAKE. The observational cohort will enroll a maximum of 440 subjects.

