#### Follow up

It is assumed that the subjects will be in the hospital up to at least 1 week after the surgery. On days 5, 6 and 7 after T0 (visits 6, 7 and 8, respectively), applicable assessments will be performed to assess study endpoints, including AKI (based on SCr). After end of all the procedures of visit 5, subjects can be discharged at the discretion of the investigator. If the subject is discharged before day 7, visit 8 will be done on the day of discharge and no site visits are required after discharge up to day 7. If the subject is discharged after day 7, visit 8 will be done on day 7 and no additional assessments are required after day 7 up to discharge, but the last result of SCr before discharge from local laboratory testing will be collected. Following day 7 (visit 8) or discharge, subjects will be followed up on day 30 (visit 9) and 90 (visit 10) following surgery. On visits 9 and 10 a composite endpoint of major adverse

kidney events (MAKE), including all-cause mortality, RRT and/or  $\geq 25\%$  sustained reduction in eGFR will be assessed.

Total number of hospital days and ICU days during initial hospitalization will be recorded. If the subjects are readmitted to hospital for any reason during the 90 follow-up days, the total number of hospitalizations and number of days hospitalized through day 30 and 90 will be recorded.

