### 6.1.2 Secondary Efficacy Endpoints

1. Proportion of subjects developing AKI (any stage) based on SCr criteria from the KDIGO guideline within 7 days after T0 (i.e., until Visit 8) (AKI-SCr7d).

[SCr evaluation visit: baseline, Visit 3, 4, 5, 6, 7 and 8 (24 hours, 48 hours, 72 hours after T0, and Day 5, 6 and 7/DoD). If the hospital discharge is earlier than Day 7, then the visits prior to DoD and Visit 8 (DoD) will be used.]

- If the subject meets at least one of the following conditions, then the subject will be treated as developing AKI-SCr7d.
  - Increasing in SCr  $\geq 0.3 \text{ mg/dL}$  within any 48 hours until Visit 8; and/or,
  - Increasing in SCr  $\geq 1.5$  times baseline until Visit 8.

2. Proportion of subjects developing AKI based on all captured criteria from the KDIGO guideline within 72 hours after T0 (AKI-KDIGO72h).

[SCr evaluation visit: baseline, Visit 3, 4 and 5 (24, 48, 72 hours after T0)]

[UO evaluation visit: Visit 3, 4, and 5 (0-12 hours, 12-24 hours, 0-24 hours, ..., and 48-60 hours, 60-72 hours and 48-72 hours after T0)]

- If the subject meets at least one of the following conditions, then the subject will be treated as developing AKI-KDIGO72h.
  - Increasing in SCr  $\geq 0.3$  mg/dL within any 48 hours until Visit 5;
  - Increasing in SCr  $\geq 1.5$  times baseline until Visit 5; and/or,
  - Urine volume  $< 0.5$  ml/kg per hour for any one of 12 consecutive hours until Visit 5 (i.e., 0-12 hours after T0, 12-24 hours after T0, ..., or 60-72 hours after T0).
- 3. Proportion of subjects developing AKI based on all criteria from the KDIGO guideline within 7 days after T0 (AKI-KDIGO7d).

[SCr evaluation visit: baseline, Visit 3, 4, 5, 6, 7 and 8(24 hours, 48 hours, 72 hours after T0, and Day 5, 6 and 7/DoD). If the hospital discharge is earlier than Day 7, then the visits prior to DoD and Visit 8 (DoD) will be used.]

[UO evaluation visit: Visit 3, 4, 5, 6, 7 and 8 (0-12 hours, 12-24 hours, 0-24 hours, ..., and 120-132 hours, 132-144 hours and 120-144 hours after T0). If the hospital discharge is earlier than Day 7, then the visits prior to DoD and Visit 8 (DoD) will be used.]

  - If the subject meets at least one of the following conditions, then the subject will be treated as developing AKI-KDIGO7d.
    - Increasing in SCr  $\geq 0.3$  mg/dL within any 48 hours until Visit 8;
    - Increasing in SCr  $\geq 1.5$  times baseline until Visit 8; and/or,

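### Time to AKI-SCr7d censors an AKI-free early discharge on the discharge day if Visit 8 was done, but carries the same subject to Day 7 if it was not

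*SAP*

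**What the plan says.** SAP 7.4.4 (Group 4) sets the censoring rule for time to AKI-SCr7d in one sentence, which opens: "For AKI-SCr7d, subjects without developing AKI-SCr7d will be censored at the date of Visit 8 (Day 7/DoD), at Day 7 if the Visit 8". Its second limb, the Day 7 date, covers a subject who has no Visit 8 result and has not left follow-up. Its third limb censors anyone who leaves the study earlier on the date of leaving. SAP Section 8 records that the censoring definition for time to AKI-SCr was added in version 4.00.

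The Visit 8 date is not fixed. Protocol 2.2.1 and the synopsis (Follow-up) allow early discharge: "After end of all the procedures of visit 5, subjects can be discharged at the discretion of the investigator". In that case "visit 8 will be done on the day of discharge and no site visits are required after discharge up to day 7". The schedule gives Visit 8 a window of 4 to 7 days. The only statement on length of stay is "It is assumed that the subjects will be in the hospital up to at least 1 week after the surgery".

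The secondary endpoint AKI-SCr7d (SAP 6.1.2) handles the same subject differently: "If the hospital discharge is earlier than Day 7, then the visits prior to DoD and Visit 8 (DoD) will be used". Only a subject who meets a creatinine criterion is an event ("then the subject will be treated as developing AKI-SCr7d"), so an AKI-free early discharge stays in the denominator as a non-event.

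For Group 4 the SAP plans Kaplan-Meier quartiles and median with 90% intervals, a log-rank test, and a Cox model with treatment as the only covariate. SAP 7.1 adds the cumulative event rate and a plot.

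**The concern.** Two things look wrong.

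- **The rule is inconsistent.** Take two subjects, both discharged on Day 5 without AKI and both still in follow-up. The one with a discharge-day creatinine is censored on Day 5. The one without it is credited as AKI-free to Day 7. Less information earns more event-free time.
- **Discharge is unlikely to be unrelated to AKI risk.** Kaplan-Meier treats a subject censored at discharge as having the later AKI risk of those who remain in hospital, and no covariate in the planned models explains discharge. If AKI after Day 4 occurs mainly in those kept in, the curve rises above the observed proportion.

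At stake is the reported level of the curve. A Day 7 cumulative rate or a median could appear that contradicts the AKI-SCr7d table in the same report.

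**Working it through.** **Inputs from the documents.** SAP Section 4: 110 per arm, placebo AKI-SCr72h 60%, relative risk 0.7 (so 0.7 × 60% = 42% on ASP1128), one-sided 0.05, about 10% drop-out. The documents give no figure for time to AKI-SCr7d; the stated 80% power is the only figure that uses these event rates.

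**Reproducing it.** 110 × 0.9 = 99 per arm; pooled proportion 0.51.
z = [0.18 − 1.645·√(2·0.51·0.49/99)] / √[(0.60·0.40 + 0.42·0.58)/99] = (0.18 − 0.1169)/0.0699 = 0.903, so power is 81.7%. This agrees with 80% to within 2 points, so 60% and 42% are used below.

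**Assumptions (not in the documents).** A fraction L of those AKI-free at 72 h develops AKI on Days 5-7, evenly and all in hospital. Of the other AKI-free subjects, cumulative fractions c4, c5, c6 have left by Days 4, 5 and 6.

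**Formula.** Per AKI-free subject at 72 h, the number at risk on day k is r_k = 1 − (1−L)·c_(k−1) − (L/3)·(k−5), for k = 5, 6, 7. The conditional Kaplan-Meier survival is S = ∏(1 − (L/3)/r_k); the value matching AKI-SCr7d is 1 − L. The arm difference is 18·S points under Kaplan-Meier and 18·(1−L) as observed, so it shrinks by the fraction 1 − S/(1−L).

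**Example, L = 15%, c = 20/40/60%.** r = 0.83, 0.61, 0.39. S = (1−0.0602)(1−0.0820)(1−0.1282) = 0.752.
- Placebo: Kaplan-Meier 1 − 0.40·0.752 = 69.9%; observed 1 − 0.40·0.85 = 66.0%.
- ASP1128: Kaplan-Meier 1 − 0.58·0.752 = 56.4%; observed 1 − 0.58·0.85 = 50.7%.
- Difference: 13.5 against 15.3 points, 11.5% smaller.

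**Shrinkage of the Day 7 difference (%).**

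| Early discharge by Day 4/5/6 | L = 5% | 10% | 15% | 20% |
|---|---|---|---|---|
| 3.3/6.7/10% | 0.4 | 0.7 | 1.1 | 1.5 |
| 10/20/30% | 1.3 | 2.6 | 4.0 | 5.3 |
| 10/30/50% | 2.6 | 5.1 | 7.6 | 10.2 |
| 20/40/60% | 4.0 | 7.8 | 11.5 | 15.1 |
| 20/50/75% | 6.8 | 13.1 | 19.0 | 24.5 |

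With L = 0 every entry is 0.

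**Median.** At L = 10% the observed ASP1128 proportion is 1 − 0.58·0.90 = 47.8%. Kaplan-Meier gives 48.2% with 10% early discharge, 49.2% with 30% and 51.9% with 60%, so a median appears only in the last case. In 3,000 simulated trials (99 per arm, 15% late risk among those staying), the ASP1128 median was reached with observed AKI below 50% in 12% of runs at 30% early discharge and 19% at 50%.

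**A different late-AKI assumption.** Let late AKI be the same share of each whole arm (6%) instead. With 50% of the AKI-free discharged early, Kaplan-Meier gives 69.8% and 51.6% against 66.0% and 48.0%. Both curves rise (3.8 and 3.6 points), but the difference is 18.2 against 18.0 points, so it does not shrink.

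**Does the Day 7 credit cause the disagreement?** Let 10% of AKI-free subjects lack Visit 8, with 6% late AKI and no early discharge. Carrying them to Day 7 gives 66.0% and 48.0%, identical to AKI-SCr7d under SAP 6.1.2. Censoring them at Day 4 gives 66.7% and 48.7%.

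**Comparison of arms.** Mean simulated log-rank z, SAP rule against carrying to Day 7:

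| Early discharge, ASP1128 / placebo | Late risk among those staying | SAP rule | Carried to Day 7 |
|---|---|---|---|
| 30% / 30% | 15% | −2.35 | −2.35 |
| 50% / 50% | 15% | −2.38 | −2.38 |
| 50% / 30% | 15% | −2.43 | −2.52 |
| 70% / 30% | 25% | −2.57 | −2.86 |

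**The case against.** The strongest defence is that nobody observes creatinine between discharge and Day 7, so censoring at the last assessment is a standard choice. Carrying subjects to Day 7 assumes no AKI in that gap. If discharged subjects keep some risk, the overstatement is smaller than computed; if they keep the same risk as those in hospital, Kaplan-Meier is right. That stands as a caution about calling the observed proportion the truth. It does not rescue the present rule, which applies last-assessment censoring to discharged subjects with a sample and abandons it for those without. AKI-SCr7d already makes the no-AKI assumption.

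It is also fair that the protocol expects about a week in hospital, that the analysis is exploratory, and that AKI-SCr7d is tested separately by the CMH method.

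A reader might infer several stronger things that the documents do not support:

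- **That the Day 7 credit for a missing Visit 8 drives the curves away from AKI-SCr7d.** Under SAP 6.1.2 it brings them into agreement. It conflicts only where missing status counts as an event, as in Protocol 7.4.2 and 7.10 and the SAP 7.4.2 sensitivity analysis. SAP 7.9.1 leaves some doubt about the main rule, but that is a separate matter.
- **That the treatment comparison is materially biased.** That needs discharge timing to differ by arm, for which there is no evidence.
- **That early discharge means a well patient.** The protocol says only that it is at the investigator's discretion.
- **That time to AKI-SCr72h has the same fault.** Discharge is allowed only after Visit 5 procedures, so a missed Visit 5 sample adds about a day and no informative discharge arises.

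**Conclusion.** The point holds as a minor defect in an exploratory analysis. The inconsistency follows from the text alone and needs no assumption. The upward shift of the Day 7 estimate needs both early discharges and later in-hospital AKI, and the documents give neither rate. Near the protocol's premise (10-30% leaving early) the difference between arms shrinks by about 0.4-5%; at 50-75% it shrinks by about 3-25%. Both ranges assume that late AKI is the same fraction of AKI-free subjects in each arm. The upper figures should not be quoted as the expected effect. With similar discharge timing in the two arms the log-rank test and hazard ratio are essentially unchanged, and nothing here touches the primary or secondary analyses.

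**What to change.** Replace the AKI-SCr7d censoring sentence in SAP 7.4.4 with one rule that matches SAP 6.1.2:

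- AKI-free subjects discharged alive before Day 7 are carried to Day 7 as event-free, whether or not the discharge-day sample was taken.
- AKI-free subjects still in the study with a missed Visit 8 stay at Day 7, as now.
- Only subjects who leave the study are censored at discontinuation.

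One minus Kaplan-Meier at Day 7 then equals the AKI-SCr7d proportion apart from discontinuations. Report censoring at the last creatinine, applied to everyone, as a sensitivity analysis. Leave the AKI-SCr72h rule as it is.

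The cost is one SAP sentence, its program and one extra run; no new data are needed. The small downside is the assumption of no AKI between the last creatinine and Day 7, which AKI-SCr7d under SAP 6.1.2 already makes.

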## 6.1 Efficacy Endpoints

### 6.1.1 Primary Efficacy Endpoint

Proportion of subjects developing AKI (any stage) based on SCr criteria from the KDIGO guideline within 72 hours after T0 (AKI-SCr72h).

[SCr evaluation visit: baseline, Visit 3, 4 and 5 (24, 48, 72 hours after T0)]

- If the subject meets at least one of the following conditions, then the subject will be treated as developing AKI-SCr72h.
  - Increasing in SCr  $\geq 0.3 \text{ mg/dL}$  within any 48 hours until Visit 5; and/or,
  - Increasing in SCr  $\geq 1.5$  times baseline until Visit 5.

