    - Urine volume  $< 0.5$  ml/kg per hour for any one of 12 consecutive hours until Visit 6 (i.e., 0-12 hours after T0, 12-24 hours after T0, ..., or 84-96 hours after T0).
19. Severity of AKI within 72 hours after T0
  - Severity of AKI based on AKI-SCr stages (Stage 1, 2, 3 or no AKI. No AKI means subject not developing AKI-SCr72h.)

- Severity of AKI based on AKI-UO stages (Stage 2, 3, or no AKI. No AKI means subject not developing AKI-UO)
- Severity of AKI based on most severe of AKI-SCr or AKI-UO stages (Stage 1, 2, 3 or no AKI)

20. Severity of AKI (based on AKI stage using SCr and/or UO) within 7 days after T0

21. Duration of AKI based on AKI stage using SCr

- Duration of AKI-SCr72h: time from moment of first meeting criteria for AKI-SCr72h until moment of first not meeting the criteria for AKI-SCr72h, death or hospital discharge. If the duration of AKI-SCr72h exceeds day 7 the time of ending of AKI will be assessed retrospectively on day 30 (visit 9) based on local SCr laboratory results. The date and value when respective criteria of AKI-SCr72h were resolved is recorded in the eCRF as an unscheduled event with check of “First NOT meeting the criteria for AKI-SCr72h/7d (SCr  $\geq$ 1.5 times baseline) before hospital discharge, if the duration of AKI-SCr72h/7d exceeds Visit 8 (Day 7).”.
- The duration will be calculated as follows;  
(Date of first not meeting the criteria, death or hospital discharge – Date of first meeting the criteria) in days.  
For subjects who don't occur AKI-SCr72h, the duration of AKI will be treated as 0.
- Duration of AKI-SCr7d (definition as above)

22. Time to AKI-SCr72h (i.e., the time from T0 to the time when criteria for AKI-SCr72h are met). The time to AKI-SCr72h will be calculated as: (Date of first meeting the criteria – Date of T0 + 1) in days.

23. Time to AKI-SCr7d (definition as above)

24. Proportion of subjects with AKI as defined by a 50% or higher reduction in eGFR based on the cystatin-C equation within 72 hours after T0.

- If the subject meet the following condition, then the subject will be treated as with AKI for this endpoint.
  - At least one of eGFR based on cystatin-C equation within 72 hours after T0  $\leq$  50% of the baseline value.

25. Proportion of subjects with AKI as defined by a 50% or higher reduction in eGFR based on the cystatin-C equation within 7 days after T0.

- If the subject meet the following condition, then the subject will be treated as with AKI for this endpoint.

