## **7 STATISTICAL METHODOLOGY**

### **7.1 General Considerations**

- For continuous variables, descriptive statistics will include the number of subjects (n), mean, standard deviation (SD), median, minimum and maximum. The number of digits to be used for the mean, standard deviation and median will be added one more digit to raw data with rounding off. The minimum and maximum will be presented with the same number of digit(s) as raw data. In addition, for pharmacokinetics (PK) variables, the coefficient of variation (CV) and the geometric mean will also be calculated.

Frequencies and percentages will be displayed for categorical data. Percentages by categories will be based on the number of subjects with no missing data, i.e. will add up to 100%. Frequencies and percentages will be rounded to one decimal place. For time-to-event variables, the number and percentage of subjects with the event using Kaplan-Meier method, the cumulative event rate will be estimated and a plot will be constructed.

- Summaries based on FAS and PPS (e.g. disposition, baseline and efficacy data) will be presented by planned randomization arm, unless specifically stated otherwise. Safety analysis and other summaries based on SAF will be presented by actual treatment received. Analysis of Observational Cohort based on PFAS will be presented by prognostic factor analysis arm.
- All statistical comparisons will be made using two sided tests at the  $\alpha=0.10$  significance level unless specifically stated otherwise. All null hypotheses will be of no treatment difference, all alternative hypotheses will be two-sided, unless specifically stated otherwise.
- All data processing, summarization, and analyses will be performed using SAS® Version 9.4 or higher on Red Hat Enterprise Linux. Specifications for Table, Figures, and Listings can be found in the TLF specifications for this study.
- For continuous variables that are recorded as “ $<X$ ”, “ $\leq X$ ”, “ $>X$ ”, or “ $\geq X$ ”, the value of “ $X$ ” will be used in the calculation of summary statistics if otherwise noted. The original values will be used for the listings.
- MedDRA will be used as the coding dictionary for adverse event and medical history.
- WHODrug Global B3 will be used as the coding dictionary for previous and concomitant medication.
- For the definition of subgroups of interest please refer to [Section [7.8](#)].

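### Time to AKI falls on a handful of whole-day values, but the exploratory Cox model names no method for ties; under Breslow the hazard ratio would be drawn towards 1

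*SAP*

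**What the plan says.** SAP 6.1.3, item 22, works from calendar dates: "The time to AKI-SCr72h will be calculated as: (Date of first meeting the criteria – Date of T0 + 1) in days". Item 23 applies the same rule to the seven-day endpoint: "Time to AKI-SCr7d (definition as above".

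The creatinine schedule limits when either endpoint can be met. For AKI-SCr72h, SAP 6.1.1 lists "SCr evaluation visit: baseline, Visit 3, 4 and 5 (24, 48, 72 hours after T0", that is, three post-baseline draws. For AKI-SCr7d, SAP 6.1.2 lists "baseline, Visit 3, 4, 5, 6, 7 and 8 (24 hours, 48 hours, 72 hours after T0, and Day 5, 6 and 7/DoD", up to six. SAP 7.11.3 bases analyses on the CRF visit.

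SAP 7.4.4, Group 4, then plans Kaplan-Meier estimates, a test ("Time to event will be analyzed using the log-rank test") and a hazard ratio with 90% CI from a "Cox proportional hazards model with treatment as the only explanatory variable". SAP 7.1 names the software ("All data processing, summarization, and analyses will be performed using SAS") without any option for ties. Protocol 7.4.4 plans only Kaplan-Meier and log-rank for these endpoints, so the SAP is the only document that defines the hazard ratio. The third Group 4 endpoint, time to ventilator weaning, is measured in hours from date and time (SAP 6.1.3, item 28).

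**The concern.** A Cox partial likelihood treats time as continuous, with ties as an occasional nuisance. Here about half of all subjects are expected to have the event, and their event times take about three distinct values (about six at seven days). A draw that slips to another calendar date adds a value but leaves the ties heavy.

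With ties this dense, the result depends on how they are handled. The Breslow approximation keeps every tied case in the risk set for all the tied events at a visit, which pulls the estimate towards 1. Efron largely removes this. A discrete (conditional-logistic) likelihood estimates a different quantity, an odds ratio. Two programmers following the same SAP text could therefore report noticeably different hazard ratios from identical data. At stake is the size of an exploratory effect estimate.

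**Working it through.** **Inputs.** SAP 4: 110 per arm, placebo AKI proportion 60%, relative risk 0.7 (so 42% on ASP1128), 1-sided 0.05, dropout about 10%. SAP 6.1.1 and 6.1.2: three and up to six draws. The split of events over visits is in neither document and is assumed below.

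**The plan's own figure.** The documents give no hazard ratio. The only stated figure that uses these rates is the 80% power. With 110 × 0.9 = 99 evaluable per arm and pooled proportion 0.51:

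(0.18 × √99 − 1.645 × √(2 × 0.51 × 0.49)) / √(0.60 × 0.40 + 0.42 × 0.58) = (1.791 − 1.163) / 0.695 = 0.903, giving power 81.7%.

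This is consistent with the stated 80%, so the planning rates are read correctly.

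**Target hazard ratio.** Under proportional hazards, ln(1 − 0.42) / ln(1 − 0.60) = ln 0.58 / ln 0.40 = 0.594, with log −0.520.

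**Expected ties.** 110 × 0.60 = 66 placebo events and 110 × 0.42 = 46.2 on ASP1128, about 112 in all, on about three distinct times.

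**Breslow equation.** With D events at a visit, N1 and N0 at risk on ASP1128 and placebo, and θ the hazard ratio, the estimate solves: total ASP1128 events = Σ D × N1θ / (N1θ + N0).

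Even spread of hazard, expected counts: 29.0, 21.3, 15.7 on placebo and 18.3, 15.2, 12.7 on ASP1128. At θ = 0.631:
- Visit 3: 47.3 × 0.631 / 1.631 = 18.3
- Visit 4: 36.5 × 57.9 / (57.9 + 81.0) = 15.2
- Visit 5: 28.4 × 48.3 / (48.3 + 59.7) = 12.7

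The sum is 46.2, as required, so Breslow returns 0.631 when the true value is 0.594. The equation scales with sample size, so using 99 per arm instead of 110 does not change this.

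**AKI-SCr72h, 1000 simulated trials per spread.** 110 per arm, no early censoring. Entries are geometric means; losses come from unrounded values.

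| Share of cumulative hazard at Visits 3/4/5 (assumed) | Breslow | Loss of log HR | Efron | Discrete (odds ratio) |
|---|---|---|---|---|
| even | 0.628 | 10.5% | 0.593 | 0.555 |
| 60/30/10 | 0.644 | 15.4% | 0.595 | 0.539 |
| 80/15/5 | 0.666 | 21.9% | 0.599 | 0.518 |
| 10/30/60 | 0.642 | 14.6% | 0.599 | 0.551 |

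On expected counts, Breslow gives 0.631, 0.647, 0.669 and 0.640. A grouped proportional-hazards (complementary log-log) model gives 0.594 for all four spreads. Breslow lay closer to 1 than Efron in more than 99% of simulated trials.

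**Limiting case.** With all events at one visit, 112.2 × θ / (1 + θ) = 46.2, so θ = 46.2 / 66 = 0.70. Breslow then returns the risk ratio.

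**AKI-SCr7d.** Six draws, same 60% and 42% assumed, expected counts: Breslow 0.613 (even) and 0.625 (40/25/15/10/5/5). The losses are 1 − ln 0.613 / ln 0.594 ≈ 6% and 1 − ln 0.625 / ln 0.594 ≈ 10%. Efron gives 0.596 and 0.597.

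**Against the noise (AKI-SCr72h).** The mean Breslow standard error of the log hazard ratio was 0.193. The shift is 0.105 × 0.520 = 0.055 to 0.219 × 0.520 = 0.114, or about 0.28 to 0.59 of one standard error. Coverage of the 90% interval was 89% to 93%.

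**The case against.** The strongest reply is that the documents never name Breslow. Silence allows Efron equally, and with Efron there is almost nothing to correct. SAP 7.1 also sends output detail to separate TLF specifications, which are not available here and might settle the matter. This stands: the bias is conditional, and a reader who infers that the reported hazard ratio will be attenuated goes further than the documents allow.

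A reader might also infer that the hazard ratio would look weaker than the risk ratio on the same data. It would not: 0.63 to 0.67 is further from 1 than the planned risk ratio of 0.70, and even the limiting case only reaches 0.70. The shortfall is against the proportional-hazards value of 0.594.

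Nor is the confidence interval invalid. It is centred somewhat closer to 1, but its coverage stays near nominal and the shift is well under one standard error.

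Finally, these are exploratory endpoints. Conclusions on AKI-SCr72h and AKI-SCr7d rest on the CMH test and the Mantel-Haenszel risk ratio (SAP 7.4.1 and 7.4.2), and the sample size and futility rule use proportions. This stands too, and it keeps the point minor.

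The reply does not justify leaving the choice open. The ties come from the visit schedule and can be foreseen. The SAP fixes imputation seeds and procedure options elsewhere (SAP 7.4.1.2), and its version 4.00 added censoring rules for these same endpoints.

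**Conclusion.** The point holds as a minor one. For the two AKI endpoints a continuous-time Cox model is planned for data with about three or six event times, and no tie method is given.

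If Breslow were used, the AKI-SCr72h hazard ratio at the planning rates would be about 0.63 to 0.67 instead of 0.594, a loss of about 11% to 22% of the log hazard ratio. AKI-SCr7d would give about 0.61 to 0.63. Efron gives about 0.59 to 0.60.

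These figures assume proportional hazards, the planned 60% and 42% (carried over to seven days without support in the documents), no early censoring, and the assumed spreads over visits. Events concentrated at one visit produce the larger losses.

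The log-rank test, the primary CMH analysis, the stated power and time to ventilator weaning are essentially unaffected.

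**What to change.** In SAP 7.4.4, Group 4, add one sentence for time to AKI-SCr72h and time to AKI-SCr7d only. The hazard ratio and 90% CI should come from a grouped proportional-hazards model (complementary log-log link, scheduled visit as a factor, treatment as covariate), or from a Cox model with Efron or exact continuous-time tie handling. The grouped model matches the way the data arise and recovered 0.594 in the check; Efron was adequate; the exact continuous-time likelihood was not computed here.

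State that the discrete (conditional-logistic) option is not to be used. It estimates an odds ratio, 0.52 to 0.56 in the check, which would overstate the effect if labelled a hazard ratio. The log-rank test and the ventilator-weaning model can stay as written.

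The cost is one code option, or one short model statement, and one SAP sentence. No data collection or sample size changes.
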